SNP – single nucleotide polymorphism

STEMI – ST-segment elevation myocardial infarction

TIMI – thrombolysis in myocardial infarction (study group)

Appendix B

SNPs Planned for Investigation

Gene	SNP	Identifier	Possible genotypes and their proportion in the population (reference and alternative)
ADD1 – α -adductin	1378 G>T (Gly460Trp)	rs4961	G=0.806737; T=0.193263
AGT – angiotensinogen	704 T>C (Met235Th)	rs699	A=0.545132; G=0.454868
	521 C>T (Thr174Met)	rs4762	G=0.878133; A=0.121867
AGTR1 – angiotensin II receptor type 1	1166 A>C	rs5186	A=0.721723; C=0.278277
AGTR2 – angiotensin II receptor type 2	1675 G>A	rs1403543	G=0.478265; A=0.521735
CYP11B2 – cytochrome 11b2 – aldosterone synthase	-344 C>T	rs1799998	A=0.573264; G=0.426736
GNB3 – beta 3 subunit of G protein – guanine-binding protein	825 C>T	rs5443	C=0.668330; T=0.331670
eNOS – nitric oxide synthase	-786 T>C	rs2070744	C=0.34927; T=0.65073
	894 G>T (Glu298Asp)	rs1799983	T=0.31468; G=0.68532
EDN1 – endothelin 1	594 G>T (Lys198Asn)	rs5370	G=0.780864; T=0.219136
F2 – prothrombin	20210 G>A	rs1799963	G=0.98867; A=0.01133

Gene	SNP	Identifier	Possible genotypes and their proportion in the population (reference and alternative)
F5 – proaccelerin	1691 G>A (Arg506Gln)	rs6025	G=0.951; A=0.049
F7 – proconvertin	10976 G>A (Arg353Gln)	rs6046	G=0.882035; A=0.117965
F13 – fibrinase	103 G>T (Val34Leu)	rs5985	G=0.786; T=0.214
FGB – fibrinogen	-455 G>A	rs1800790	G=0.81485; A=0.18515
ITGA2- α 2 – integrin	807 C>T (Phe224Phe)	rs1126643	C=0.610691; T=0.389309
ITGB3- β 3 – integrin	1565 T>C (Leu33Pro)	rs5918	T=0.851958; C=0.148042
SERPINE1 (PAI-1) – serpin	-675 5G>4G	rs1799762	4G=0.48510; 5G=0.51490
MTHFR – methylenetetrahydrofolate reductase	677 C>T (Ala222Val)	rs1801133	G=0.659842; A=0.340158
	1298 A>C (Glu429Ala)	rs1801131	T=0.695830; G=0.304170
MTR – B12 dependent methionine synthase	2756 A>G (Asp919Glu)	rs1805087	A=0.808600; G=0.191400
MTRR – methionine synthase reductase	66 A>G (Ile22Met)	rs1801394	A=0.482820; G=0.517180

Statistical Analysis Plan

Study Title:	Genetic Determinants of the Coronary Microvascular Obstruction in Percutaneous Coronary Interventions
Protocol Number:	CMVO-SNP-2022
Study Number:	NCT05355532
Document date and version:	Version number 1 from April 24, 2022
Sponsor:	Privolzhsky Research Medical University
Principal Investigator:	
Principal Investigator: [name] [name]
 
Research Center: State Budgetary Healthcare Institution of Nizhny Novgorod Region "City Clinical Hospital No. 13 of Avtozavodsky District of Nizhny Novgorod"
 
Research Center Address: [name]
 
Research Center [contact]

1. Primary Objective: to identify statistically significant associations between selected SNPs and CMVO development post-PCI in STEMI patients.

2. Data Preparation

2.1 Data Collection

- Genetic data: SNP genotypes (binary: variant present/absent)
- Clinical data:
 - demographics
 - angiographic parameters
 - laboratory values
 - procedural details
 - hospitalization outcomes
 - CMVO presence/absence

2.2 Data Cleaning

- Missing data: exclude samples with >10% missing SNP calls.
- Quality control: Hardy-Weinberg equilibrium testing ($p < 0.05$ threshold for exclusion)

3. Statistical Methods

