Identifying genetic determinants of CMVO holds significant scientific novelty and could form the basis for a novel diagnostic system to predict this complication. Such a system would be clinically valuable, reducing PCI-related risks and improving patient outcomes.

Study Objective: to identify genetic determinants of coronary microvascular obstruction development during percutaneous coronary interventions.

Study Design

A matched case-control study will be conducted to examine the role of specific single nucleotide polymorphisms (SNPs) as predictors of coronary microvascular obstruction (CMVO) development. The study will enroll 80 patients meeting the inclusion/exclusion criteria who have provided written informed consent. Patients will be allocated into two groups in a 1:1 ratio:

- Group 1 (CMVO+): 40 patients with myocardial infarction (MI) who developed CMVO following PCI
- Group 2 (CMVO-, control group): 40 patients with MI who did not develop CMVO following PCI

Group allocation will be performed by the principal investigator. The groups will be matched by sex and age using the "matched pairs" method [9]. For each patient in the CMVO+ group, a corresponding patient of the same sex and similar age (± 5 years) will be selected from the pool of MI patients who underwent PCI without CMVO development.

The required sample size (80 patients) was determined based on the following parameters: alpha error level – 5 %, study power – 80 %, group ratio – 1:1, minimum detectable odds ratio – 4.0, expected prevalence of the studied SNPs in the population: 12–69 % (average 50%) [10]. Among the 40 planned matched pairs, 20 pairs must be discordant (i.e., the paired patients must differ in the presence or absence of the predictor).

The study will be conducted in several stages:

1. Patient Screening

- The principal investigator will assess inclusion/exclusion criteria.
- Determine eligibility for study group allocation.
- Performed in the catheterization laboratory immediately after PCI completion.

2. Informed Consent Process

- Eligible patients will provide written informed consent for genetic testing.

- Patients will be assigned to respective study groups.
- Conducted in the catheterization laboratory.

3. Biological Sample Collection

- Blood sampling for genetic analysis.
- Performed in the catheterization laboratory.

4. Sample Processing and Transportation

- Blood sample processing.

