- Transportation to the Central Research Laboratory of the Institute of Fundamental Medicine at Privolzhsky Research Medical University (Russian Ministry of Health).

5. Clinical Data Collection

- The investigator will complete patient registry forms.
- Includes hospitalization course and outcomes.

6. Genetic Analysis

- Performed at the Central Research Laboratory of the Institute of Fundamental Medicine at Privolzhsky Research Medical University.

7. Data Management

- Collected information will be entered into a unified electronic database.

8. Statistical Analysis

- Comprehensive processing of all obtained data.

Ethical Information About the Study

The study is conducted in accordance with Good Clinical Practice (GCP) standards and the principles of the Helsinki Declaration. The study protocol has been approved by the local ethics committee. Patient information is processed anonymously. Upon inclusion in the study, each patient is assigned a serial number. The following data are recorded in the registry of enrolled patients: serial number, last name, first name, patronymic, sex, date of birth, study group, date of inclusion in the study, medical record number, contact phone number, home address, pair number. This registry is stored at the research center. The serial number is indicated on: the

inclusion/exclusion criteria form; the patient's voluntary informed consent for study participation; blood collection tubes with patient samples; the patient registry form with hospitalization details and outcomes; the unified electronic database of study participants. All work with blood samples outside the research center and statistical processing of obtained data is performed in anonymized form.

Inclusion Criteria:

1. Signed voluntary informed consent for study participation by the patient;
2. Male or female aged 18 years or older;
3. ST-segment elevation myocardial infarction (STEMI) type I according to the Fourth Universal Definition of Myocardial Infarction criteria [11] and current clinical guidelines for this condition [12];
4. Enrollment in the study immediately after PCI with possibility of blood sampling in the catheterization laboratory after signing informed consent;
5. For "CMVO+" group: Development of CMVO as a result of PCI (CMVO is assessed according to criteria specified in the European Society of Cardiology clinical guidelines) [12];

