3.2 Sensitivity Analysis

- Re-run analysis using dominant/recessive genetic models

4. Outcome Measures

- Primary endpoint: CMVO
- Secondary endpoints:
 - In-hospital mortality

- Left Ventricle Ejection Fraction
- Ventricular fibrillation
- N-terminal Pro-brain Natriuretic Peptide
- Six-minute Walk Test

5. Statistical Software

- R

6. Sample Size Justification

- 80 patients (40 CMVO+/40 CMVO-) provides:
 - 80% power to detect $OR \geq 4.0$ ($\alpha=0.05$, two-tailed)
 - Assumes SNP prevalence = 12–69% (average 50%)

7. Data Presentation

- Tables:
 - Baseline characteristics (Me [Q1; Q3] for continuous; n (%) for categorical)
 - SNP frequencies by group
 - Multivariate ORs for CMVO predictors
- Figures:
 - Flowchart of patient inclusion
 - Forest plot of significant SNPs

8. Ethical Considerations

- All analyses will use anonymized data (patient serial numbers only).
- Protocol deviations documented in CONSORT flowchart.
- Approval:

Local Ethics Committee Protocol Version: 1.0

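### SAP 2.2 makes no sex-linked exception to its Hardy-Weinberg exclusion rule, so a sound AGTR2 rs1403543 would probably be dropped if men and women are tested together

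*SAP*

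**What the plan says.** SAP 2.2 (Data Cleaning) has two lines. The first removes samples with too many missing calls. The second is the filter at issue: "Hardy-Weinberg equilibrium testing ($p < 0.05$ threshold for exclusion". It does not say whether controls or all patients are tested, which version of the test is used, or how sex is handled.

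The SNP table in Protocol Appendix B has 22 entries. One is for "AGTR2 – angiotensin II receptor type 2", rs1403543, with frequencies "G=0.478265; A=0.521735". It is laid out like the other 21, with no note on chromosome or sex.

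Protocol Inclusion Criteria item 2 admits both sexes: "Male or female aged 18 years or older". Under Study Design, "The groups will be matched by sex and age", so cases and controls contain the same share of men. Neither document states what that share is expected to be.

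SAP 2.1 codes genotypes as variant present or absent. SAP 3.2 repeats the analysis under dominant and recessive models. Neither mentions men who carry a single copy.

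**The concern.** A Hardy-Weinberg filter treats a shortage of heterozygotes as a sign of bad genotyping. For an X-linked SNP, men have one copy. An assay that reports which of two alleles is present shows them as homozygous, so no man can be a heterozygote. A sample that mixes the sexes is therefore short of heterozygotes by construction, however good the laboratory work.

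The filter would then discard a valid candidate SNP rather than a faulty assay, and would do so before McNemar's test or conditional logistic regression is run. This differs from the 5% loss that a p < 0.05 threshold imposes on any sound SNP. It is specific to this locus and grows with the share of men.

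**Working it through.** **The plan's own sample size, reproduced first.** Inputs (Protocol, Study Design; SAP 6): two-sided alpha 0.05, power 80%, odds ratio 4.0, SNP prevalence 50%.

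- P = OR/(1 + OR) = 4/5 = 0.8
- Discordant pairs = [1.960/2 + 0.842 × √(0.8 × 0.2)]² / (0.8 − 0.5)² = 19.26, rounded up to 20
- Exposure in cases = 4 × 0.5/(1 + 3 × 0.5) = 0.8
- Discordant fraction = 0.5 × 0.2 + 0.8 × 0.5 = 0.5
- Pairs = 20/0.5 = 40

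This agrees with the stated 80 patients and 20 discordant pairs. The sample size is not in question here. It fixes n = 40 per group for the next step.

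**Expected heterozygote deficit.** Inputs: q(A) = 0.521735 and p(G) = 0.478265 (Appendix B); n = 40 if controls are tested, 80 if all patients are; m = share of men. Three assumptions come from outside the documents: AGTR2 is X-linked, the sexes are pooled, and m takes the values shown.

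- Heterozygotes expected under Hardy-Weinberg: n × 2pq = n × 0.4991
- Heterozygotes expected in the pooled sample: n × (1 − m) × 2pq, since only women can be heterozygous
- Inbreeding coefficient: F = 1 − (1 − m) = m
- Chi-square on 1 degree of freedom: about nF² = nm²

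Example, all 80 patients with 70% men: 12.0 heterozygotes expected against 39.9 under Hardy-Weinberg, and nm² = 80 × 0.49 = 39.2 against a critical value of 3.84. Setting nm² = 3.84 gives the share of men at which the typical result reaches the threshold: √(3.84/40) = 31% in 40 controls and √(3.84/80) = 22% in all 80.

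**Probability of exclusion.** The nm² approximation is rough at these sizes (at n = 40 and 50% men it gives 89%), so the figures below come from simulation: 20,000 samples per setting, error-free calls, men read as homozygotes, women drawn under Hardy-Weinberg. Each cell shows the chance of p < 0.05 by chi-square / exact test.

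| Share of men | 40 controls, pooled | All 80, pooled | Women among the 40 controls only |
|---|---|---|---|
| 0% | 5% / 3% | 5% / 4% | 5% / 3% |
| 20% | 18% / 17% | 41% / 41% | 5% / 3% |
| 30% | 42% / 39% | 79% / 79% | 5% / 3% |
| 40% | 72% / 69% | 98% / 98% | 6% / 4% |
| 50% | 94% / 92% | >99.9% / >99.9% | 5% / 2% |
| 60% | 99.7% / 99.5% | about 100% | 7% / 2–3% |
| 70% | about 100% | about 100% | 5% / 2% |
| 80% | about 100% | about 100% | 7% / 2% |

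Testing women only brings the loss back to about the nominal level. At 90% men only 4 women remain among the controls; the chi-square figure is then 12% and the exact figure 0%, so the exact test is the safer choice.

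**What remains if the SNP is kept.** Carrier coding, OR 4, 40 pairs:

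- Male pairs: control exposure 0.522, case exposure 4 × 0.522/(1 + 3 × 0.522) = 0.814, discordant fraction 0.486
- Female pairs: control exposure 1 − 0.478265² = 0.771, case exposure 0.931, discordant fraction 0.266
- At 50% men: 40 × (0.5 × 0.486 + 0.5 × 0.266) = about 15 discordant pairs, power about 68%
- At 80% men: 40 × (0.8 × 0.486 + 0.2 × 0.266) = about 18 discordant pairs, power about 76%

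The association test is therefore usable for this SNP, a little below the planned 80% power.

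**The case against.** The strongest reply is that the SAP prescribes no wrong test. It is silent on sex, and a women-only test of this SNP fits its wording. X-linkage, pooling and the share of men all come from outside the text. That stands as a limit on how firmly the point can be put. It does not remove the point: the rule as worded is general, nothing directs the analyst to treat one of 22 loci differently, and the plain application is one test per SNP in the sample. It can also be said that the line does not name what is excluded. But Hardy-Weinberg is a property of a SNP, and the line before it already deals with samples, so removal of the SNP is the natural reading.

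A reader might go further in four ways that the documents do not support.

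- *Loss of the SNP is a near certainty.* That needs pooling plus roughly 60% men in 40 controls, or 40–50% in all 80. At 30% men the figures are 42% and 79%. No share of men is given.
- *The study cannot answer its question.* At most one of 22 candidates is affected. Its genotypes are still collected and the filter can be corrected before analysis. Nor does the SAP say that a failure would be reported as a genotyping fault.
- *This SNP is especially valuable because its alleles are the most balanced or its power among the best.* Appendix B has two more balanced SNPs, SERPINE1 (0.48510/0.51490) and MTRR (0.482820/0.517180), and power here is about 68–76% at 50–80% men.
- *The SAP 3.2 re-run is invalid in men and should use female pairs only.* Dominant and recessive codings coincide in men, but male pairs contribute validly to both. At 70–80% men only 8–12 female pairs remain, with about 2–3 discordant under the dominant model (8 × 0.266 = 2.1; 12 × 0.266 = 3.2). An exact McNemar test needs at least 6 discordant pairs, all in one direction, to reach p < 0.05 (2 × 0.5⁶ = 0.031; with 5 it is 0.063).

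**Conclusion.** The concern holds in conditional form. If AGTR2 is X-linked and the sexes are pooled, the SAP 2.2 rule is likely to remove a correctly genotyped rs1403543 once men make up about 40% or more of the sample: 72% or more in 40 controls and 98% or more in all 80, by chi-square, against a nominal 5%. At 30% men the risk is still 42% and 79%. The consequence is the loss of one pre-selected SNP of 22 before its association test. The other 21 SNPs and the overall objective are untouched. The plan should be changed, because the rule contains no safeguard and the repair is simple.

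**What to change.** First confirm the chromosomal location from the rs number; dbSNP is already the protocol's source for SNP prevalence. Then amend the SAP:

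- **SAP 2.2:** test Hardy-Weinberg for AGTR2 rs1403543 in women only, preferably by the exact test, and do not exclude it on a mixed-sex test. Name the group tested (controls or all patients).
- **SAP 2.1:** code men at this SNP as hemizygous, variant present or absent.
- **SAP 3.1 and 3.2:** keep male pairs in McNemar's test, conditional logistic regression and the dominant/recessive re-run. These stay valid because both members of a pair have the same sex. Add a note that the two codings coincide in men, so the two models differ only through female pairs.

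The cost is a few sentences. Sex is already recorded and no new data are needed. The drawback is a weaker quality check. With 70% men, 40 controls include 12 women, and a genuine deficit of F = 0.3 gives a noncentrality of only 12 × 0.3² = 1.08, so real genotyping problems at this SNP could pass unnoticed.

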3.1 Statistical Analysis

- Univariate analysis:
 - McNemar's test (matched case-control design) for categorical SNPs
 - Odds ratios (OR) with 95% confidence intervals
- Multivariate analysis:
 - Conditional logistic regression
 - OR with 95% confidence intervals

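### Twenty-two SNPs are tested one by one with no multiplicity rule; if none matters, the first pass still yields a false determinant with probability 41–66%, and the forest plot shows only the significant ones

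*SAP*

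**What the plan says.** SAP 1 sets the primary objective: "to identify statistically significant associations between selected SNPs and CMVO development post-PCI in STEMI patients". Protocol Appendix B lists the SNPs; counting the rows with an rs identifier gives 22, in 19 genes. SAP 2.1 codes each as "SNP genotypes (binary: variant present/absent"). SAP 3.1 then applies "McNemar's test (matched case-control design) for categorical SNPs", with odds ratios and 95% confidence intervals, followed by conditional logistic regression. It does not say which version of McNemar's test is used.

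SAP 3.2 adds "Re-run analysis using dominant/recessive genetic models" without saying whether a re-run can count as a finding.

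The only alpha given for association is 5%, two-sided, in the sample-size text (Protocol, Study Design; SAP 6), tied to 80% power at an odds ratio of 4. The Protocol adds: "Among the 40 planned matched pairs, 20 pairs must be discordant".

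SAP 7 plans a "Forest plot of significant SNPs" and, without that restriction, a table of "SNP frequencies by group". Neither document names a primary SNP, an adjusted threshold, a false-discovery rule, an exploratory status or a replication step.

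**The concern.** The objective is met by any SNP that reaches significance, and the plan gives 22 first-pass chances with no control over the whole set. The study could therefore report a genetic determinant of CMVO although none of the SNPs matters. The Protocol's Study Rationale looks ahead to a diagnostic system built on such determinants, so a false one has consequences.

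Three gaps add to this:

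- The McNemar version is open, and could be chosen after the data are seen.
- The recessive re-runs are extra tests with no stated status. If present/absent means carrying at least one variant allele, the main analysis is already the dominant model, so the recessive runs are what SAP 3.2 adds.
- A forest plot filtered on significance shows odds ratios that are too far from 1 on average.

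**Working it through.** **Inputs.** 40 pairs, two-sided 0.05, odds ratio 4 and prevalence averaging 50% (Protocol, Study Design; SAP 6); 22 variant frequencies q (Protocol, Appendix B); present/absent coding (SAP 2.1). My assumptions: 0.05 is the threshold for each test; present means at least one variant allele; Hardy-Weinberg proportions; independent loci; genotypes independent within pairs; all 40 pairs analysable.

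**The plan's own figure.** With odds ratio 4, P = 4/5 = 0.8. Discordant pairs needed = (1.96/2 + 0.8416 × √(0.8 × 0.2))² / 0.3² = 19.3, rounded up to 20. At control prevalence 0.5 the case prevalence is 0.8, so the discordant fraction is 0.5 × 0.2 + 0.8 × 0.5 = 0.5, giving 40 pairs. The stated size is reproduced as a single test at 0.05. Nothing in it allows for 22 tests.

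**First-pass error.** For each SNP, carrier prevalence c = 1 − (1 − q)², and under the null the discordant fraction is d = 2c(1 − c). The number of discordant pairs is Binomial(40, d). The rejection probability of each McNemar version is averaged over that distribution, and the SNPs are combined as 1 − ∏(1 − size). Two examples:

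- MTHFR 1298: q = 0.304, c = 0.516, so 40d is about 20.0 discordant pairs. Attained size is 5.3% uncorrected, 3.0% exact, 2.7% continuity-corrected.
- F2: q = 0.01133, c = 0.0225, so 40 × 2 × 0.0225 × 0.9775 = 1.8 discordant pairs. Attained size is 1.0%, 0.02%, 0.02%.

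Sizes differ this much, so the shortcut 1 − 0.95²² = 67.6% is not used.

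| Quantity | Uncorrected | Exact | Continuity-corrected |
|---|---|---|---|
| No SNP matters, first pass: at least one false positive | 66.4% | 45.2% | 41.0% |
| Expected number of false positives | 1.06 | 0.59 | 0.52 |
| Same chance if recessive re-runs may create findings (simulated) | 83% | 58% | 54% |
| The same, one SNP kept per gene | 78% | 52% | 49% |
| One true SNP at odds ratio 4: mean false share of declared SNPs (no declaration counted as zero) | 43% | 29% | 26% |
| The same, only among datasets that declare something | 46% | 34% | 32% |
| Mean false share under Benjamini-Hochberg at 5% | 3% | 2% | 1% |
| The same, only among datasets that declare something | 8% | 7% | 5% |
| Power for one SNP, odds ratio 4, prevalence 50%, at 0.05 | 82% | 74% | 73% |
| Power for that SNP at 0.05/22 | 34% | 27% | 27% |
| Power for one true SNP under Benjamini-Hochberg | 33% | 27% | 26% |

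The one-true-SNP rows take MTHFR 1298 as the true SNP.

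**Forest plot.** With 20 discordant pairs the smallest significant split is 15:5 under all three versions, an odds ratio of 15/5 = 3.0. If the true odds ratio is 1.5, the split follows Binomial(20, 0.6). Given at least 15, 59% of results sit exactly at 15:5, so the median shown is 3.0, twice the truth. If the true odds ratio is 4, the split follows Binomial(20, 0.8). The median significant split is then 17:3, shown as 5.7, and 22% of significant estimates fall below 4.

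**The case against.** The missing rule is not in dispute; the objections concern the percentages and the remedy.

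- **Coding.** Carrier coding is inferred. If present meant homozygous, the first-pass range would be 23–52%. That reading is strained, and the figure would still be far above 5%.
- **Linkage and the Hardy-Weinberg filter.** AGT, eNOS and MTHFR each contribute two SNPs. Keeping one per gene gives 61% / 40% / 36%. The filter in SAP 2.2 would remove about 22 × 0.05 = 1.1 SNPs, lowering the figures by a few points. So 41% is not a strict floor.
- **The regression.** The SAP does not say whether the McNemar tests or the conditional logistic model defines a reported determinant, and the figures describe only the former. But the model comes with no SNP-selection or error-control rule, so it is no safeguard as written.
- **How many SNPs are real.** The SNPs were chosen on mechanism, so several could matter. With three true SNPs at odds ratio 4 the unadjusted false share falls to 25% / 17% / 16%, and with five to 18% / 12% / 11%. The one-true-SNP row is one scenario.
- **Selective display.** Only the forest plot is restricted; the frequency table is not, though it is not said to carry odds ratios. The 15:5 threshold is for 20 discordant pairs, and most SNPs expect fewer under the null.
- **The remedy.** Benjamini-Hochberg is one choice among several. A written exploratory label with a replication requirement would also address the misleading claim. This stands: the plan needs a stated error rule or a stated exploratory status, and it has neither.

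**Conclusion.** The concern holds and should be fixed before the analysis. On carrier coding with 22 independent loci and 40 complete pairs, a study with no true SNP declares at least one in its first pass with probability 41–66%. The unnamed McNemar version alone accounts for 66.4 − 41.0 = 25.4 percentage points. One SNP per gene gives 36–61%; no reading examined brings the chance near 5%. If recessive re-runs may create findings, it rises to 54–83%. With one true SNP at odds ratio 4, 26–43% of declared SNPs are false on average, and with three, 16–25%.

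The absence of a rule and the single-test basis of the sample size are certain. The exact percentages depend on the stated assumptions, including that 0.05 is the test threshold. The filtered forest plot is a secondary but separate defect.

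**What to change.** - **SAP 3.1:** make present/absent coding the single primary test per SNP, and define it. Name the McNemar version, for example exact, since F2 expects fewer than 2 discordant pairs. Apply Benjamini-Hochberg at a 5% false discovery rate across all SNPs tested. Reserve the words significant and determinant for SNPs that pass. Report unadjusted p-values beside the adjusted ones, labelled as candidates needing replication.
- **SAP 3.2:** state that re-runs under other genetic models are supportive and cannot create a finding.
- **SAP 6:** state that the 80% power is for one SNP at unadjusted 0.05, and give the power under the adjusted rule for the chosen McNemar version.
- **SAP 7:** show all SNPs tested in the forest plot, with 95% confidence intervals.

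The cost is wording in four sections and one line of R, with no extra patients. The real price is stated power: for one SNP at odds ratio 4 it falls from 73–82% to 26–33% under Benjamini-Hochberg. Holding 80% at 0.05/22 would need 38.6, so 39, discordant pairs: 39/0.5 = 78 pairs, or 156 patients. That enlargement is not requested, which is why the unadjusted results should stay visible as candidates.

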STUDY PROTOCOL

Genetic Determinants of the Coronary Microvascular Obstruction in Percutaneous Coronary Interventions

Study Title:	Genetic Determinants of the Coronary Microvascular Obstruction in Percutaneous Coronary Interventions
Protocol Number:	CMVO-SNP-2022
Study Number:	NCT05355532
Document date and version:	Version number 1 from April 24, 2022
Sponsor:	Privolzhsky Research Medical University
Principal Investigator:	
Principal Investigator: [name] [name]
 
Research Center: State Budgetary Healthcare Institution of Nizhny Novgorod Region "City Clinical Hospital No. 13 of Avtozavodsky District of Nizhny Novgorod"
 
Research Center Address: [name]
 
Research Center [contact]

Study Rationale

For decades, ischemic heart disease (IHD) has been the leading cause of mortality in developed countries. Currently, percutaneous coronary intervention (PCI) is the primary method for restoring blood flow in the coronary artery (CA) in IHD, significantly reducing mortality in myocardial infarction (MI) and improving quality of life in stable angina. However, in 5–10% of cases, PCI leads to coronary microvascular obstruction (CMVO, or "no-reflow")—a phenomenon characterized by the absence of adequate myocardial perfusion despite successful restoration of epicardial coronary artery patency [1]. CMVO substantially worsens prognosis and can be a direct cause of death [1].

The pathogenesis of CMVO is complex and involves multiple concurrent mechanisms with varying degrees of contribution [1]. The most significant clinically established predictors of CMVO include: age, time from symptom onset to reperfusion, severity of acute heart failure (Killip classification), ineffective prehospital thrombolytic therapy, collateral blood flow (Rentrop classification) [6], coronary artery thrombus burden (TIMI thrombus grade) [7], baseline coronary flow (TIMI flow grade) [8], implantation of ≥ 3 stents during PCI, direct stenting of the target artery, blood neutrophil and glucose levels [2–5].

The pathophysiological heterogeneity of CMVO makes its prediction challenging. Even the best available models [2–5] demonstrate limited positive predictive value (60–70%). This limitation may stem from the omission of genetic factors influencing endothelial function, microcirculation, hemostasis, and inflammation in current models.

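### The 80% power covers only the single-SNP McNemar test; the multivariable conditional logistic regression on the same 40 pairs is unsized and unlimited, and by ordinary likelihood it overstates odds ratios more with each added term

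*SAP*

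**What the plan says.** - **Sizing.** The protocol (Study Design) gives "alpha error level – 5 %, study power – 80 %, group ratio – 1:1, minimum detectable odds ratio – 4.0" and adds: "Among the 40 planned matched pairs, 20 pairs must be discordant". It explains discordance as the two patients differing on a single predictor. SAP 6 repeats the claim as "80% power to detect" an OR of at least 4.0, two-sided, and does not name the test.
- **Analyses.** SAP 3.1 lists McNemar's test with ORs and 95% intervals as the univariate analysis. The multivariate analysis is "Conditional logistic regression", also with ORs and 95% intervals. It gives no covariates, selection rule, limit on terms, estimator, test or handling of separation.
- **Output.** The only table of ORs in SAP 7 is "Multivariate ORs for CMVO predictors". A forest plot of significant SNPs is also planned, without saying which ORs it shows.
- **Candidates.** The protocol's Study Rationale says: "The most significant clinically established predictors of CMVO include: age, time from symptom onset to reperfusion", and goes on to list 11 items in all. Age is matched, which leaves 10. The SNP appendix lists 22 SNPs. The registry card records CMVO risk factors for later analysis.

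**The concern.** In a 1:1 matched design each pair contributes one within-pair comparison, so the model has 40 units of information, not 80. As coefficients are added, the ordinary conditional maximum-likelihood estimate moves away from 1, and eventually some fits have no finite solution. This happens with common predictors; it does not need rare variants.

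The SAP therefore permits anything from a nearly harmless small model to one that roughly doubles the OR, and the choice could be made after the data are seen. At stake are inflated ORs with very wide intervals in the multivariable table, and a real OR-4 SNP that loses significance after adjustment. The rationale attributes the limits of current prediction models to missing genetic factors, so a model that combines SNPs with the clinical predictors is a natural one to fit.

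**Working it through.** **1. Reproducing the 80%.** Inputs from the documents: two-sided alpha 0.05, power 0.80, OR 4.0, average SNP prevalence 50%, 40 pairs.

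- Control prevalence 0.5 is odds of 1, so case odds are 4 and case prevalence is 0.8.
- Probability that a pair is discordant: 0.8 × 0.5 + 0.2 × 0.5 = 0.5, so 20 of 40 pairs.
- Among discordant pairs, the share with the exposed case is 4/(4 + 1) = 0.8.
- Discordant pairs needed: [1.96/2 + 0.8416 × √(0.8 × 0.2)]² / 0.3² = (0.980 + 0.337)² / 0.09 = 19.3, or about 38.5 pairs in all.
- The exact test with 20 discordant pairs has 80.4% power.

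The plan's figure reproduces, as a calculation for one binary predictor.

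**2. Size of the multivariable model.** With one SNP and the 10 unmatched clinical predictors at one coefficient each, there are 11 coefficients on 40 pairs: 40/11 = 3.6 pairs per coefficient. With one SNP and 2 covariates the ratio is 40/3 = 13.3.

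**3. Simulation.** A 1:1 conditional logistic model is a no-intercept logistic model on within-pair differences. Settings: 40 pairs, SNP prevalence 50% in controls, true OR 4. Assumptions not in the documents: covariates independent of the SNP, mainly binary at 40% prevalence, one coefficient each, one SNP per model. There were 600 to 4,000 runs per scenario for ordinary likelihood. Medians are essentially those of finite fits; non-finite fits count as non-significant in the Wald power. Ranges span separate sets of runs.

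| Covariates added to the SNP | Their effect | Median SNP OR | Wald power |
|---|---|---|---|
| 0 | – | 4.0 | 75–77% |
| 2 | none or prognostic | 4.4–4.5 | 69–76% |
| 3 | none | 4.6–4.7 | 75–76% |
| 5 | none | 5.1–5.2 | 73–74% |
| 5 | OR 2 each | 5.4 (5.6 in one set) | 56–58% |
| 10 | none | about 7–8 | 64–67% |
| 10 | OR 1.5 each | about 7–8 | 43–46% |
| 10 | OR 2 each | 7.6 | 14–15% |

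With 10 covariates, no finite fit is obtained in about 5% (no effect), 13–14% (OR 1.5) and 41–43% (OR 2). If the non-finite fits are kept in the median, the 10-covariate no-effect OR is 8.2–8.5.

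**4. Likelihood-ratio test.** With 10 no-effect covariates it rejects in 78–79%, but its type I error is 11–12%. With the critical value corrected to 5%, power is about 64%. Changing the test does not restore the 80%.

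**5. Firth-penalised conditional likelihood, same settings.** The median OR is about 3.7–3.9 at every model size (one set of runs gave 3.5–3.8), with type I error of about 3–7%. In the three 10-covariate scenarios, profile-test power is 68%, 54% and 38% (500 runs).

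**The case against.** The strongest objection concerns attribution. A reader might infer that the planned model is overfitted and that its power is 65% or less. The documents do not support that. The 10 predictors appear in the rationale as background on published models; neither they nor the risk factors on the registry card are named as covariates. A model with 2 or 3 covariates fits the SAP equally well and has modest bias (about 4.4–4.7). The power figure also depends on a Wald test that the SAP does not specify. Part of the gap from 80% is the test itself, since Wald power is already 75–77% with the SNP alone. Ordinary maximum likelihood is likewise only the default reading. All of this stands.

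A reader might also infer that the SAP applies its 80% to the multivariable table. It does not say so. The primary objective is SNP association, McNemar's test is listed first, and the sizing matches it. Unadjusted ORs are already planned in SAP 3.1. SAP 6 simply does not say which analysis its figure covers.

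These points narrow the claim but do not remove it. No text prevents a large model, and the bias grows with every term. The comparison of Firth profile tests with ordinary Wald tests mixes estimator and test, so the case for penalisation rests mainly on bias and type I error, not on a gain in power.

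**Conclusion.** The concern holds in conditional form. The 80% is a single-SNP McNemar figure, correctly calculated, and the multivariable model is neither sized nor limited. Under ordinary likelihood a true OR of 4 is overstated by roughly a tenth with 2 covariates (4.5/4 = 1.13) and by about 75–100% if all 10 listed predictors were entered (7/4 = 1.75; 8/4 = 2.0). In that last case Wald power is about 64–67% when the predictors have no effect. It is lower when they are prognostic, which is the more realistic case because the protocol calls them established.

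The sizes rest on the assumed SNP prevalence of 50%, on independence of SNP and covariates, and on one coefficient per covariate. Entering the ordinal angiographic or Killip grades as categories would add terms and make matters worse. The McNemar analysis is unaffected. The change is worth making because it is cheap and corrects most of the bias at any model size.

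**What to change.** - **SAP 3.1:** fit the multivariable model by Firth-penalised conditional logistic regression (equivalently, penalised no-intercept logistic regression on within-pair differences), with profile penalised-likelihood tests and 95% intervals. Name a short covariate list and a maximum number of coefficients for 40 pairs before the genotype data are analysed.
- **SAP 6:** state that the 80% refers only to the unadjusted single-SNP McNemar test and that adjusted ORs are supportive.
- **SAP 7:** show the unadjusted matched OR beside each adjusted OR.

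The cost is SAP wording only. The method is available in R, the software that the SAP already names, and no extra patients or data are needed. The downsides are slight shrinkage toward 1 (about 3.7–3.9 for a true 4), fewer covariates adjusted for at once, and a narrower power statement. Penalisation does not bring a large model back to 80% power. How many covariates to allow, and whether SNPs may enter jointly, are trade-offs for the sponsor to settle and write down.
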